## **5.2 Titration Visit(s) (TV1, TV2, TV3, TV4, TV5, TV6)**

Eligible subjects who enter directly into SP848 (without prior participation in SP847 or another applicable LCM primary study) will initiate treatment with LCM at TV1, and the LCM dose will be titrated over the following week(s). Titration Visits are not applicable for subjects who have participated in SP847 or another LCM primary study; the first visit in SP848 for these subjects is Visit 1 (see Section 5.3).

At TV1, subjects who have enrolled directly into SP848 will receive a single dose of LCM (1mg/kg [oral solution] or 50mg [tablet]) during the clinic visit. Over the following days, subjects will be administered LCM 1mg/kg bid (oral solution) or LCM 50mg bid (tablet), and will begin titrating in weekly increments of 2mg/kg/day (oral solution) or 100mg/day (tablet) up to a level to optimize tolerability and seizure control (not to exceed 12mg/kg/day [or 600mg/day based on body weight, whichever is lower]). Subjects must be on each LCM dose for at least 5 days before titrating up to the next dose. It should be noted, in cases of incomplete doses (eg, subject spits out all or a portion of the syrup), missed doses, or administration of an erroneous volume of syrup, study medication should not be readministered and these cases would not be considered dose reductions. The LCM dose titration steps are summarized in Section 4.4.1.2.

A total of up to 6 Titration Visits may be required (eg, for a subject whose dose is titrated to the maximum permitted dose of LCM 12mg/kg/day). However, based on tolerability and seizure control, a subject's LCM dose may be titrated to a lower dose level; in such a case, fewer than 6 Titration Visits would be required.

The following assessments are required for each TV:

- Concomitant medications assessment
- Concomitant AEDs assessment
- Brief physical examination
- Brief neurological examination
- 12-lead ECG (2 interpretable recordings approximately 20 to 30 minutes apart prior to vital signs assessment and collection of any blood samples)

- Vital signs assessment (blood pressure and pulse)
- Body weight
- Blood sample for clinical chemistry, hematology, and endocrinology (TV4 only)
- Urine sample for urinalysis (TV4 only)
- LCM return/compliance (as applicable)
- Subject diary assessment
- C-SSRS
- Adverse event reporting
- Health care resource use
- Dispense subject diary
- Dispense LCM (as applicable)

All subjects will be required to have an ECG (2 interpretable recordings) conducted at LCM maximum plasma concentration ( $C_{max}$ ) 1 week after an initial LCM dose increase to a LCM dose level that is  $\geq 8\text{mg/kg/day}$  or a new concomitant AED is introduced. Subjects will be required to arrive at the clinic prior to taking their morning dose of LCM. Subjects will be administered their morning LCM dose by study personnel at the clinic so that an ECG (2 interpretable recordings approximately 20 to 30 minutes apart prior to vital signs assessment) can be performed 30 minutes to 1 hour after the administration of LCM (ie, at LCM steady state  $C_{max}$ ).

### 5.3 Visit 1 (Week 0)

For subjects who completed SP847, Visit 1 for SP848 was the same as Day 2 of the second PK collection time period (which may include an overnight stay at a hospital or medical facility) in SP847 (Day 28 for Cohorts 1, 2, 3, and 5 with maximum recommended dose of 8mg/kg/day; Day 35 for Cohorts 2 to 5 with maximum recommended dose of 10mg/kg/day; and Day 42 for Cohorts 2 to 5 with maximum recommended dose of 12mg/kg/day). For subjects who discontinued SP847 due to a dose reduction or status epilepticus, Visit 1 was the Early Termination Visit in SP847. For subjects in SP847 who were titrated up to the maximum permitted dose of 600mg/day sooner than the study schedule would ordinarily indicate (based on body weight) and who enroll in SP848, the Early Termination Visit of SP847 also served as Visit 1 for SP848.

For subjects who enroll in SP848 after participation in other LCM pediatric clinical studies besides SP847 (ie, SP0966 and EP0060) in epilepsy, SP848 Visit 1 will be specified in the respective primary study protocol.

For subjects who enter directly into SP848 (without prior participation in SP847 or other LCM pediatric clinic studies in epilepsy), the LCM dose will be titrated at weekly intervals as described in Section 4.4.1.2 and Section 5.2. These subjects will reach Visit 1 either (1) when the LCM dose is titrated to a level that, in the opinion of the investigator, optimizes tolerability and seizure control, or (2) when the maximum permitted LCM dose is reached (12mg/kg/day [or 600mg/day based on body weight, whichever is lower]). In the case of a subject who requires a dose reduction during the Titration Visits, the subject's LCM dose will be returned to the

previous dose level and the next clinic visit will be Visit 1 at the reduced level. Visit 1 should occur at least 5 days after the final TV. At Visit 1, the progress in SP848 for subjects who entered directly into SP848 and for subjects who have enrolled from SP847 or other LCM pediatric clinical studies in epilepsy will be aligned; subsequent regularly scheduled clinic visits for all subjects will be at 4-week intervals as outlined in the following sections.

The informed consent process for SP848 will be conducted at Visit 1 for subjects who have not previously been through the informed consent process at the Screening Visit (ie, subjects enrolling from SP847 or other LCM pediatric clinical studies in epilepsy for whom Visit 1 is the first study visit in SP848). Prior to the conduct of any study-related procedures, a complete explanation (both verbally and written) of the nature and purpose of the study will be given to the subject (when possible or as required according to local IRBs/IECs) and the subject's parent/legal guardian by the investigator (or designee). The subject's parent/legal guardian will be requested to sign and date the IRB/IEC-approved Informed Consent Form. When possible, or as required by local IRB/IEC, the subject will be requested to give assent to participate in the study.

Each subject's eligibility will be determined on the basis of the inclusion/exclusion criteria and the results of the following assessments (applicable only for subjects for whom Visit 1 is the first clinic visit for SP848), and a complete medical history update will be obtained. If available, the data for the following assessments will be taken from the last assessment during SP847 (or other primary study, as applicable):

- Concomitant medications assessment
- Concomitant AEDs assessment
- Complete physical examination
- Complete neurological examination
- 12-lead ECG (2 interpretable recordings approximately 20 to 30 minutes apart prior to vital signs assessment but 30 minutes to 1 hour after the administration of LCM)
- Vital signs assessment (blood pressure and pulse)
- Body weight and height assessment
- Blood sample for clinical chemistry, hematology, and endocrinology
- Blood sample for LCM and concomitant AED plasma concentrations
- Urine sample for urinalysis
- Serum pregnancy test for female subjects of childbearing potential
- Tanner Stage assessment (if applicable)
- Clinical Global Impression of Change
- Caregiver Global Impression of Change
- C-SSRS

- Achenbach CBCL to be completed by the parent(s)/legal representative(s) (CBCL/1½-5 for children from 18 months to 5 years 11 months and CBCL/6-18 for children 6 years and older) (subjects enrolling from SP847 or another applicable LCM pediatric clinical study in epilepsy)
- Bayley-III scales for children <18 months of age enrolled in English-speaking countries (subjects enrolling from SP847 or another applicable LCM pediatric clinical study in epilepsy)
- BRIEF-P/BRIEF score (if applicable)
- PedsQL score (if applicable)
- Adverse event reporting
- Health care resource use
- Dispense subject diary (to assess seizure frequency, document the intake of concomitant AEDs, and record AEs for the following 4 weeks)
- Dispense LCM. Subjects and caregivers (including parent/legal guardian) will be instructed to administer LCM at approximately 12-hour intervals (once in the morning and once in the evening).

#### **5.4 Telephone contacts (Weeks 2, 6, 10, 16, 24, 32, 40, 48, 66, and 78)**

Between scheduled clinic visits, the investigator (or designee) should contact the subject's caregiver (including parent/legal guardian) by telephone. The investigator (or designee) should remind the subject's caregiver (including parent/legal guardian) to ensure the diary is completed and to bring unused LCM to the next clinic visit. The following should be performed via telephone:

- Concomitant medications assessment
- Concomitant AEDs assessment
- Adverse event reporting

If an AE necessitates the subject's withdrawal from the study, the subject should return for an Early Termination Visit ([Section 5.17](#)) as soon as possible.

Lacosamide is supplied so that the subject or caregiver (including parent/legal guardian) can immediately decrease their dose, if needed, in consultation over the telephone with the investigator or subinvestigator. Thus, LCM can be continued at a decreased dose until a clinic visit can be scheduled.

#### **5.5 Visit 2 (Week 4)**

During Visit 2 (Week 4), the following will be performed:

- Concomitant medications assessment
- Concomitant AEDs assessment
- Brief physical examination

- Brief neurological examination
- 12-lead ECG (2 interpretable recordings approximately 20 to 30 minutes apart prior to vital signs assessment and collection of blood sample)
- Vital signs assessment (blood pressure and pulse)
- Body weight and height assessment
- Blood sample for clinical chemistry and hematology
- Blood samples for LCM and concomitant AED plasma concentrations (at any time post-dosing with LCM)
- Urine pregnancy test for female subjects of childbearing potential
- LCM return/compliance. Subject's caregivers will be instructed to return unused LCM at each study visit. Returned medication will be reconciled by the investigator (or designee) in order to monitor the subject's compliance with the medication schedule. If a subject is found to be noncompliant, a decision will be made by the investigator, in conjunction with UCB BIOSCIENCES, as to whether the subject should be withdrawn from the study.
- Subject diary assessment
- C-SSRS
- Adverse event reporting
- Health care resource use
- Dispense subject diary (to assess seizure frequency, document the intake of concomitant AEDs, and record AEs until the next clinic visit)
- Dispense LCM. Subjects and caregivers (including parent/legal guardian) will be instructed to administer LCM at approximately 12-hour intervals (once in the morning and once in the evening).
- A 12-lead ECG (2 interpretable recordings) is also required when the dose of LCM is increased to a LCM dose level that is  $\geq 8\text{mg/kg/day}$  or a new concomitant AED is introduced. The ECG should be performed after the increased dose of LCM or the new AED has reached steady-state. This ECG can be done at the next scheduled visit. When the ECG assessment is done, 2 interpretable recordings will be performed approximately 20 to 30 minutes apart prior to vital sign assessment and collection of blood samples (if applicable), but 30 minutes to 1 hour after the administration of LCM (if applicable).

All subjects will be required to have an ECG (2 interpretable recordings) conducted at LCM  $C_{\max}$  1 week after an initial LCM dose increase to a LCM dose level that is  $\geq 8\text{mg/kg/day}$ . This ECG can be conducted at an Unscheduled Visit, if necessary. These subjects will be required to arrive at the clinic prior to taking their morning dose of LCM. Subjects will be administered their morning LCM dose by study personnel at the clinic so that an ECG (2 interpretable recordings approximately 20 to 30 minutes apart prior to vital signs assessment) can be performed 30 minutes to 1 hour after the administration of LCM (ie, at LCM steady state  $C_{\max}$ ).

## 5.6 Visit 3 (Week 8)

During Visit 3 (Week 8), the following will be performed:

- Concomitant medications assessment
- Concomitant AEDs assessment
- Brief physical examination
- Brief neurological examination
- Vital signs assessment (blood pressure and pulse)
- Body weight and height assessment
- Urine pregnancy test for female subjects of childbearing potential
- LCM return/compliance
- Subject diary assessment
- C-SSRS
- Adverse event reporting
- Health care resource use
- Dispense subject diary (to assess seizure frequency, document the intake of concomitant AEDs, and record AEs until the next clinic visit)
- Dispense LCM. Subjects and caregivers (including parents/legal guardians) will be instructed to administer LCM at approximately 12-hour intervals (once in the morning and once in the evening).
- A 12-lead ECG (2 interpretable recordings) is also required when the dose of LCM is increased to a LCM level dose that is  $\geq 8\text{mg/kg/day}$  or a new concomitant AED is introduced. The ECG should be performed after the increased dose of LCM or the new AED has reached steady-state. This ECG can be done at the next scheduled visit. When the ECG assessment is done, 2 interpretable recordings will be performed approximately 20 to 30 minutes apart prior to vital sign assessment and collection of blood samples (if applicable), but 30 minutes to 1 hour after the administration of LCM (if applicable).
- All subjects will be required to have an ECG (2 interpretable recordings) conducted at LCM  $C_{\max}$  1 week after an initial LCM dose increase to a LCM dose level that is  $\geq 8\text{mg/kg/day}$ . This ECG can be conducted at an Unscheduled Visit if necessary. These subjects will be required to arrive at the clinic prior to taking their morning dose of LCM. Subjects will be administered their morning LCM dose by study personnel at the clinic so that an ECG (2 interpretable recordings approximately 20 to 30 minutes apart prior to vital signs assessment) can be performed 30 minutes to 1 hour after the administration of LCM (ie, at LCM steady state  $C_{\max}$ ).

## 5.7 Visit 4 (Week 12)

Assessments for Visit 4 (Week 12) are the same as those described for Visit 3 (Week 8), in Section 5.6.

## 5.8 Visit 5 (Week 20)

During Visit 5 (Week 20), the following will be performed:

- Concomitant medications assessment
- Concomitant AEDs assessment
- Complete physical examination
- Complete neurological examination
- Vital signs assessment (blood pressure and pulse)
- Body weight and height assessment
- Blood sample for clinical chemistry, hematology, and endocrinology
- Blood sample for LCM and concomitant AED plasma concentrations (at any time post-dosing with LCM)
- Urine sample for urinalysis
- Urine pregnancy test for female subjects of childbearing potential
- Clinical Global Impression of Change
- Caregiver Global Impression of Change
- LCM return/compliance
- Subject diary assessment
- C-SSRS
- Achenbach CBCL to be completed by the parent(s)/legal representative(s) (CBCL/1½-5 for children from 18 months to 5 years 11 months and CBCL/6-18 for children 6 years and older) (subjects enrolling from SP847 or another applicable LCM pediatric clinical study in epilepsy)
- Bayley-III scales for children <18 months of age enrolled in English-speaking countries (subjects enrolling from SP847 or another applicable LCM pediatric clinical study in epilepsy)
- BRIEF-P/BRIEF score (if applicable)
- PedsQL score (if applicable)
- Adverse event reporting
- Health care resource use
- Dispense subject diary (to assess seizure frequency, document the intake of concomitant AEDs, and record AEs until the next clinic visit)
- Dispense LCM. Subjects and caregivers (including parents/legal guardians) will be instructed to administer LCM at approximately 12-hour intervals (once in the morning and once in the evening).

A 12-lead ECG (2 interpretable recordings) is also required when the dose of LCM is increased to a LCM dose level that is  $\geq 8\text{mg/kg/day}$  or a new concomitant AED is introduced. The ECG should be performed after the increased dose of LCM or the new AED has reached steady-state. This ECG can be done at the next scheduled visit. When the ECG assessment is done, 2 interpretable recordings will be performed approximately 20 to 30 minutes apart prior to vital sign assessment and collection of blood samples (if applicable), but 30 minutes to 1 hour after the administration of LCM (if applicable).

All subjects will be required to have an ECG (2 interpretable recordings) conducted at LCM  $C_{\max}$  1 week after an initial LCM dose increase to a LCM dose level that is  $\geq 8\text{mg/kg/day}$ . This ECG can be conducted at an Unscheduled Visit, if necessary. These subjects will be required to arrive at the clinic prior to taking their morning dose of LCM. Subjects will be administered their morning LCM dose by study personnel at the clinic so that an ECG (2 interpretable recordings approximately 20 to 30 minutes apart prior to vital signs assessment) can be performed 30 minutes to 1 hour after the administration of LCM (ie, at LCM steady state  $C_{\max}$ ).

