## **5.12                  Visit 9 (Week 52)**

Assessments for Visit 9 (Week 52) are the same as those described for Visit 5 (Week 20), in [Section 5.8](#), with the following exception: completion of the palatability and ease of use questionnaire and a 12-lead ECG (2 interpretable recordings approximately 20 to 30 minutes apart prior to vital signs assessment and collection of blood sample) are conducted at Visit 9.

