## **5.14                  Visit 11 (Week 72)**

Assessments for Visit 11 (Week 72) are the same as those described for Visit 5 (Week 20), in [Section 5.8](#), with the following exceptions for all sites: brief physical and neurological exams are conducted (instead of complete physical and neurological exams as indicated for Visit 5), the laboratory blood sample is collected only for clinical chemistry and hematology (ie, no

endocrinology), the palatability and ease of use questionnaire is completed, and a 12-lead ECG (2 interpretable recordings approximately 20 to 30 minutes apart prior to vital signs assessment and collection of blood sample) is conducted. In addition to the noted differences, a PK sample is routinely drawn at sites in Japan (removed for all other sites).

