### **5.16 Visit 13/Termination Visit (Week 96)**

At the completion of the study, investigators should discuss treatment options with the subject and/or their parent/legal guardian to best manage the subject's epilepsy. Taper of LCM may not be required for some subjects who complete the study depending on the treatment option selected by the investigator in consultation with the subject and/or parent/legal guardian. These subjects should complete Visit 13/Termination Visit and then complete the Safety Follow-Up telephone contact 28 to 35 days after Visit 13/Termination Visit. The Final Visit is not required for subjects who complete the study and who do not undergo taper of LCM. The Safety Follow-Up Visit and the Safety Follow-Up telephone contact are not required for subjects who participate in EP0151 or EP0152.

Subjects who complete the study and discontinue use of LCM (as determined by the investigator in consultation with the subject and/or parent/legal guardian) should taper LCM gradually as described in [Section 4.4.1.3](#). These subjects should complete Visit 13/Termination Visit, followed by the Final Visit which occurs 2 weeks after the final dose of study medication, and then the Safety Follow-Up telephone contact which occurs 28 to 35 days after the last dose of LCM.

Assessments for Visit 13/Termination Visit (Week 96) are the same as those described for Visit 5 (Week 20), in [Section 5.8](#), with the following exceptions for all sites: the laboratory blood sample is collected only for clinical chemistry and hematology (ie, no endocrinology), a 12-lead ECG (2 interpretable recordings approximately 20 to 30 minutes apart prior to vital signs assessment and collection of blood sample) is conducted, a Tanner Stage assessment is conducted (if applicable), an Achenbach CBCL is conducted, Bayley-III scales are conducted, BRIEF-P/BRIEF and PedsQL scores are obtained, and the palatability and ease of use questionnaire is completed. In addition to the noted differences, a PK sample is routinely drawn at sites in Japan (removed for all other sites).

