#### **8.4.7 Achenbach CBCL**

The Achenbach CBCL is a widely used validated questionnaire to evaluate a child’s competencies and behavioral/emotional problems. Behavioral problems will be scored by the parent(s)/legal representative(s). Depending on the subject’s age, 2 versions of the CBCL will be used. The CBCL/1½-5 checklist is intended for use in children 18 months to 5 years and 11 months of age. For subjects ≥6 years to ≤17 years of age, the CBCL/6-18 version will be used.

The Achenbach CBCL will be completed according to the tabular schedule of study procedures, [Section 16.1](#).

In both questionnaires, the occurrence of certain problems and behaviors (in the past 2 months for the CBCL/1½-5 version and in the past 6 months for the CBCL/6-18 version) will be scored on the following scale:

- 0=not true (as far as known)
- 1=somewhat or sometimes true
- 2=very true or often true

Syndrome scores will be calculated from these questions, which will in turn be summarized by 2 composite scores. Additionally, for each syndrome and composite scores, categorizations based on a normative sample will be used to evaluate normal, borderline, or clinically relevant behavior.

In addition, the Achenbach CBCL/6-18 includes ratings related to performance in school, activities in leisure time, and special interests.

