##### **12.1.2.2      Other safety variables**

The other safety variables include changes in laboratory parameters (ie, hematology, clinical chemistry, endocrinology, and urinalysis), 12-lead ECG measurements, vital sign measurements (blood pressure and pulse rate), physical and neurological exam findings, body weight, height, calculated BMI, and Tanner Stage (if applicable). The actual measurement and its change from Baseline (SP847 [or other primary study as applicable] Visit 1) or the Screening Visit (for subjects who entered directly into SP848) will be analyzed descriptively and presented by visit. In addition, shift tables may be used to evaluate the number and percentage of subjects having a different post-Baseline status when compared with their Baseline status.

The shift from Baseline to the subject's last visit at which a physical and/or neurological examination was performed post-Baseline will be summarized by category.

Laboratory, ECG, and vital signs data outside of the respective reference ranges will be listed and highlighted.

Changes in behavior and development from Baseline as measured using the Achenbach CBCL for children 18 months and older (CBCL/1½-5 and CBCL/6-18) and Bayley-III scales for children <18 months of age will be summarized descriptively and presented by visit. Changes in cognitive function as measured using the BRIEF-P/BRIEF will be summarized by descriptive statistics at each visit. Baseline is defined as Visit 1 for subjects from SP847 or other epilepsy studies. Baseline values for subjects who enroll directly into SP848 will be taken from the Screening Visit.

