**Table 16–1: Schedule of study procedures for SP848 (Year 1)**

Study SP848	Year 1													Safety Follow-Up
	V1 b	TC c	V2	V3	V4	V5	V6	V7	V8	V9	ETV d	Unsch Visit e	Final Visit f	
Visit a														
Weeks in study	0		4	8	12	20	28	36	44	52				
Dispense diary	X		X	X	X	X	X	X	X	X	X			
Diary assessment			X	X	X	X	X	X	X	X	X	X	X	
C-SSRS p	X h		X	X	X	X	X	X	X	X	X	X q	X	
Achenbach CBCL	X					X				X	X			
Bayley-III scales	X					X				X	X			
BRIEF-P/BRIEF	X					X				X	X			
PedsQL	X					X				X	X			
AE reporting r	X h	X	X	X	X	X	X	X	X	X	X	X	X	X
Health care resource use	X		X	X	X	X	X	X	X	X	X	X	X	

AE=adverse event; AED=antiepileptic drug; C-SSRS=Columbia-Suicide Severity Rating Scale; ECG=electrocardiogram; ETV=Early Termination Visit; GIC=Global Impression of Change; LCM=lacosamide; PK=pharmacokinetics; TC=telephone contact; S=serum; SAE= serious adverse event; U=urine; Unsch=Unscheduled; V=Visit

Note: All subjects who directly enrolled into SP848 should follow the titration schedule in [Table 16–3](#).

- a A time window of  $\pm 7$  days relative to Visit 1 is applicable for all scheduled visits and telephone contacts (with the exception of the Safety Follow-Up telephone contact).
- b For subjects who have participated in SP847 (or other LCM pediatric clinical studies in epilepsy), Visit 1 is also the last visit of the primary study. At Visit 1, the informed consent will be signed (and assent, if applicable) and eligibility assessed, the medical history will be updated, body weight and height and concomitant medications including AEDs will be recorded, AEs will be assessed, and the subject diary and LCM dispensed.
- c Telephone contacts are scheduled during the following weeks during Year 1: Weeks 2, 6, 10, 16, 24, 32, 40, and 48.
- d An Early Termination Visit must be completed for all subjects who prematurely discontinue from the study.
- e If an Unscheduled Visit is needed, then the assessments noted will be performed. Additional assessments can be performed at the investigator's discretion. If the LCM dose is decreased between scheduled clinic visits due to an AE, or if a LCM dose increase is required between scheduled clinic visits, the subject must return for an Unscheduled Visit. Height will not be recorded at an Unscheduled Visit.

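### The visit text limits the CBCL at Weeks 20, 52 and 72 to rollover subjects, while the schedule tables require it for everyone, so CBCL follow-up of direct enrollees depends on which part a site follows

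*Protocol*

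**What the plan says.** **Visit text.** In Section 5.8 the CBCL bullet ends with a rollover restriction: "for children 6 years and older) (subjects enrolling from SP847 or another applicable LCM pediatric clinical study in epilepsy". The next bullet restricts the other scale in the same way: "Bayley-III scales for children <18 months of age enrolled in English-speaking countries (subjects enrolling from SP847 or another applicable LCM pediatric clinical study in epilepsy". Two later visits are defined by reference to this one: "Assessments for Visit 9 (Week 52) are the same as those described for Visit 5 (Week 20" (Section 5.12) and "Assessments for Visit 11 (Week 72) are the same as those described for Visit 5 (Week 20" (Section 5.14). Neither section lists the CBCL or Bayley-III among its exceptions. Section 5.16 (Week 96) does name them, without a restriction: "an Achenbach CBCL is conducted, Bayley-III scales are conducted". Section 5.17 (Early Termination Visit) also has no restriction, and Section 5.1 has direct enrollees complete the CBCL at Screening.

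**Tables.** The "Achenbach CBCL" row of Table 16-1 is marked at V1, V5, V9 and the Early Termination Visit. The same row of Table 16-2 is marked at V11, V13 and the Early Termination Visit. No footnote limits either row to rollover subjects. Section 8.4.7 points to the tables: "The Achenbach CBCL will be completed according to the tabular schedule of study procedures". Section 8.4.8 does the same for Bayley-III.

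**Analysis.** Section 12.1.2.2 summarises change from Baseline in both scales descriptively by visit. Direct enrollees take Baseline from Screening. For the others, "Baseline is defined as Visit 1 for subjects from SP847 or other epilepsy studies". Section 12.1.4.2.2 repeats this rule for the PedsQL. Section 12.1 gives a general rule for rollover subjects, Visit 1 of the primary study, unless otherwise noted.

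**The concern.** The restriction makes sense at Visit 1 (Section 5.3), because direct enrollees were tested at Screening shortly before. From Week 20 on that reason is gone. BRIEF and PedsQL are scheduled in Section 5.8 for every subject, so no burden argument for sparing direct enrollees one questionnaire is apparent.

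The CBCL is a named safety variable (Section 4.2.1.2). Direct enrollees were added to supply long-term safety exposure for regulatory submissions (Section 1). They have never received LCM (exclusion criterion 4), so their Screening CBCL is certainly a pre-LCM value. If their Week 20, 52 and 72 questionnaires are not collected, Section 12.1.5 allows no imputation and nothing replaces them.

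**Working it through.** The protocol states no figure to reproduce here. The check compares text with tables, followed by simple counts.

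**1. CBCL visits for a direct enrollee under each source**

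| Visit | Section 5 text | Tables 16-1 and 16-2 |
|---|---|---|
| V5, Week 20 | no (5.8) | yes |
| V9, Week 52 | no (5.12, via 5.8) | yes |
| V11, Week 72 | no (5.14, via 5.8) | yes |
| V13, Week 96 | yes (5.16) | yes |

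The text gives 1 of 4 scheduled post-Baseline visits and the tables give 4 of 4. The difference is 3 of 4, or 75%. Both sources add an Early Termination Visit for subjects who withdraw.

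**2. Number of direct enrollees** (Sections 1 and 12.2)

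Inputs: about 100 under Amendment 4, about 46 in Japan and about 60 additional in China, out of up to about 400 in total. The protocol does not say whether Japan's 46 fall within the 100.

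- Japan within the 100: 100 + 60 = 160, and 160/400 = 40%.
- Japan added: 100 + 46 + 60 = 206, and 206/400 = 51.5%.

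**3. Assessments at stake if every site followed Section 5, before dropout**

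- 3 × 160 = 480 of 4 × 160 = 640.
- 3 × 206 = 618 of 4 × 206 = 824.

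These are upper limits. The real number depends on how many sites follow the text and on dropout.

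**4. Bayley-III**

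The scale is for children under 18 months. Inclusion criterion 5 sets the direct-enrollee age at 4 to 17 years. No direct enrollee can take it, so the restriction loses 0 assessments.

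**5. Visit 1**

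Section 5.3 limits the CBCL and Bayley-III at Visit 1 to rollover subjects. Table 16-1 marks V1 for all without a footnote. This is the same kind of conflict, in a place where the text has a clear reason.

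**6. Rollover Baseline**

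The rule in 12.1.2.2 and 12.1.4.2.2 does not name the study. SP848 Visit 1 is the natural reading, because Section 5.3 collects these scales there. At that visit subjects coming from SP847 are already on LCM; for SP847 completers it is Day 28, 35 or 42. The other reading is the primary-study Visit 1 of Section 12.1, which an earlier paragraph of 12.1.2.2 also uses for the other safety variables.

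**The case against.** The strongest reply is that Sections 8.4.7 and 8.4.8 name the tables as the schedule, and the tables collect the data. This stands in part: total loss is not the expected outcome, and uneven collection between sites is more likely. It does not remove the conflict, because Section 5 is the visit-by-visit instruction and nothing ranks it below the tables. The tables also use footnotes elsewhere to restrict a row (Tanner Stage; LCM samples at sites in Japan), so the missing footnote here cannot be read as an implied limit.

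One could argue that Section 5.16 lists the CBCL as an exception at Week 96 because the restriction at the other visits was deliberate. But the same list names BRIEF and PedsQL, which Section 5.8 already requires for everyone. The list therefore shows no intent either way.

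A reader might infer more than the documents support:

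- **Direct enrollees are the only subjects with a pre-LCM behavioural Baseline.** This is not established. The rollover Visit 1 is unnamed, and whether a primary study collected the CBCL is not stated. The Day 28 to 42 timing applies to SP847 completers; about 42 SP847 subjects were eligible. For other rollovers, Section 5.3 leaves Visit 1 to the primary-study protocol.
- **An early behavioural effect would be invisible in rollover subjects.** This is too strong. CBCL recall is 6 months (CBCL/6-18) or 2 months (CBCL/1½-5) under Section 8.4.7. Assume that SP847 days count from the first LCM dose and that the windows are 183 and 61 days. The on-LCM share at Day 28 to 42 is then 28/183 to 42/183 (15% to 23%), or 28/61 to 42/61 (46% to 69%). An early effect would be blunted, not hidden.
- **The protocol must tabulate the enrolment routes separately.** That is tabulation detail the protocol may leave to the SAP.

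**Conclusion.** The contradiction holds for the CBCL at Weeks 20, 52 and 72. Where Section 5 is followed, direct enrollees keep only the Week 96 or early-termination value. That puts up to 480 to 618 assessments at stake, in 40% to 51.5% of about 400 subjects, assuming planned enrolment is reached and ignoring dropout. Where sites differ, Weeks 20, 52 and 72 would combine rollovers with direct enrollees from some sites only, while Week 96 covers both groups. Changes across visits would then partly reflect who was measured.

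The study is descriptive and the CBCL is not a primary variable, so no test or sample-size claim is affected. The point still deserves correction, because the data cannot be recovered later. For Bayley-III only the wording conflicts. The rollover Baseline is ambiguous as written, not shown to be wrong.

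**What to change.** 1. In Section 5.8, delete the rollover-only parenthetical from the CBCL bullet and align the Bayley-III bullet. Sections 5.12 and 5.14 then agree with Tables 16-1 and 16-2 through their cross-references.
2. Footnote the V1 cells for the CBCL and Bayley-III in Table 16-1 to say that they apply to rollover subjects, matching Section 5.3.
3. In Sections 12.1.2.2 and 12.1.4.2.2, state whether the rollover Baseline is SP848 Visit 1 or Visit 1 of the primary study.

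If the sponsor did intend fewer CBCL visits for direct enrollees, the tables need a footnote saying so, and the by-visit summary should be described as covering rollover subjects only at Weeks 20, 52 and 72.

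The cost is wording. The tables already schedule these assessments, so no new visit or instrument is needed.
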